Alpha Blockers	
 Used for BPH, OR Used for hypertension with majority of SBP < 140 mmHg OR other antihypertensives have not been tried 	
 No taper needed 	
 2 MDS assessments post intervention: MDS items pertaining to function (ADLs) Chart review at 1 and 4 months post intervention: elevated blood pressure, tachycardia, functional decline hospitalizations, ED visits 	
 Nursing will check blood pressure twice weekly during medication reduction period; report 2 or more readings of SBP > 160 mmHg to clinician. (End date for this order is the same end date of the taper) 	
 If drug therapy is ultimately necessary, try other antihypertensive (e.g., amlodipine) Alternative treatments for hypertension are unlikely to be necessary
Beta Blockers	
 Used for hypertension OR another indication aside from rate control 	
 50% dose reduction every 2 weeks to discontinuation (over a total of 8 weeks) 	
 2 MDS assessments post intervention: MDS items pertaining to behaviors, mood, function (ADLs) Chart review at 1 and 4 months post intervention: elevated blood pressure, tachycardia, behaviors, anxiety, functional decline hospitalizations, ED visits 	
 Nursing will check blood pressure twice weekly during medication reduction period; report 2 or more readings of SBP > 160 mmHg to clinician (End date for this order is the same end date of the taper) 	
 Alternative treatments are unlikely to be necessary
Other Antihypertensive Drugs (calcium channel blocker, angiotensin	
 SBP <140mmHg 	
 50% dose reduction every 2 weeks to d/c or SBP 141- 	
 2 MDS assessments post intervention: MDS items 	
 Nursing will check blood pressure twice weekly during medication 	
 Alternative treatments are unlikely to be necessary, but behavioral

converting enzyme inhibitor, or angiotensin receptor blocker)		160mmHg	
 pertaining to function (ADLs) Chart review at 1 and 4 months post intervention: elevated blood pressure, tachycardia, functional decline hospitalizations, ED visits 	
 reduction period; report 2 or more readings of SBP > 160 mmHg to MD/NP (End date for this order is the same end date of the taper) 	
 therapies like transcendental meditation or biofeedback techniques may have a role
Diuretics	
 Used for venous stasis or lymphedema, OR Used for hypertension with SBP < 140mmHg OR other classes not tried 	
 No taper needed 	
 2 MDS assessments post intervention: MDS items pertaining to function (ADLs) Chart review at 1 and 4 months post intervention: elevated blood pressure, CHF exacerbation, functional decline, hospitalizations, ED visits 	
 Nursing will check blood pressure twice weekly during medication reduction; report 2 or more readings of SBP > 160 mmHg to MD/NP. Obtain weekly weights x 4 weeks; nursing to notify MD/NP of weight gain >=5 lbs (End date for this order is the same end date of the taper) 	
 Employ compression hose May try other antihypertensive (e.g., lisinopril), especially if SBP increases to >180 mmHg or DBP increases to >100 mmHg
Proton Pump Inhibitors	
 Continuous PPI use >8 weeks, AND No long-term use of non-steroid anti-inflammatory drugs, history of bleeding stomach ulcer(s), severe inflammation of the esophagus, or Barrett's esophagus 	
 Reduce dose by half every 2 weeks (over a total of 4 weeks), OR In the case of capsules that cannot be split or broken in half, take a dose every other day for 2 weeks and then take a dose every 3 days 	
 2 MDS assessments post intervention: MDS items pertaining to behaviors, pain, function (ADLs) Chart review at 1 and 4 months post intervention: gastroesophageal reflux, functional decline hospitalizations 	
 Nursing to notify MD/NP for symptom recurrence, including heartburn, dyspepsia, regurgitation, or anorexia during medication reduction period. (End date for this order is the same end date of the taper) 	
 If heartburn, acid reflux, or rebound symptoms occur after discontinuation, elevate resident's head by using extra pillows

		for 2 weeks (over a total of 4 weeks)	ns, ED visits		
Hypoglycemics – Sulfonylureas, Meglitidines	
 • Most recent hemoglobin A1C <8.5, OR • Insulin dose is >40 units/day, OR • Patient refusing to eat or is eating irregularly 	
 • No taper needed 	
 • 2 MDS assessments post intervention: MDS items pertaining to function (ADLs) • Chart review at 1 and 4 months post intervention: severe hyperglycemia (>400), polydipsia, polyuria, functional decline hospitalizations, ED visits 	
 • Nursing will measure fasting blood twice weekly for 2 weeks. Notify MD/NP for any BG >300 or >2 values over 200. (End date for this order is the same end date of the taper) 	
 • Substitute dipeptidyl peptidase-4 inhibitor if A1C rises to >9 (Goal is to achieve hemoglobin A1C 8-9 AND no episodes of severe hypoglycemia or severe hyperglycemia)
Hypoglycemics – Sliding Scale Insulin (SSI)*	
 • Type II Diabetes, AND • SSI is the only insulin treatment, OR • SSI in addition to basal insulin, OR • SSI in addition to basal insulin and mealtime insulin 	
 • No taper needed • If most recent hemoglobin A1C <=8.5, discontinue SSI without adding treatment 	
 • 2 MDS assessments post intervention: MDS items pertaining to function (ADLs) • Chart review at 1 and 4 months post intervention: severe hyperglycemia (>400), polydipsia, polyuria, functional decline hospitalizations, ED visits 	
 • Nursing will measure fasting blood sugar daily for 2 weeks. Notify MD/NP for any BG >300 or >2 values over 200 (End date for this order is the same end date of the taper) 	
 • If most recent hemoglobin A1C >8.5, review average daily insulin requirement over prior 5–7 days, then initiate basal insulin at 50–75% of that average daily insulin requirement
		*Please see separate table for additional scenarios related to sliding scale insulin which deprescribing may be appropriate.			

Table 2. Algorithm for Prescribing Osteoporosis Treatment in NH-PRIDE study

Drug Class	Prescribing Criteria	Study Team will Monitor	Nursing will notify MD/NP for new symptoms	Treatment Options
Calcium and Vitamin D	
 • Life expectancy > 6 months based on MDS question J1400 or validated tool, and not enrolled in hospice, AND • No evidence of hypercalcemia (>10.5mg/dL) by chart review 	
 • 2 MDS assessments post intervention: MDS items pertaining to function (ADLs) • Chart review at 1 and 4 months post intervention: elevated serum calcium (>10.5mg/dL), worsening constipation, functional decline hospitalizations, ED visits 	
 • Nursing will notify MD/NP for worsening constipation 	
 • Ensure 1200mg calcium through diet and supplements. • 1000-2000IU vitamin D daily
Antiresorptives	
 • Estimated FRAiL score \geq 10% OR Estimated FRAiL score \geq 5% + history of fracture • Life expectancy >6 months based on MDS question J1400 or validated tool, and not enrolled in hospice • No contraindications (allergy, etc.) 	
 • 2 MDS assessments post intervention: MDS items pertaining to function (ADLs) • Chart review at 1 and 4 months post intervention: gastroesophageal reflux, esophagitis, injection site reactions (for subcutaneous medications), hypocalcemia (<8.7mg/dL), functional decline, hospitalizations, ED visits 	
 • Nursing will assure proper administration of oral bisphosphonates (taken on empty stomach, sit upright for at least 30 minutes afterwards). • Nursing will notify MD/NP for worsening indigestion, injection site reactions (for subcutaneous medications) 	
 • Oral bisphosphonate • IV bisphosphonate • SQ denosumab

Table 3. Sliding Scale Insulin (adapt from Munshi et al. *Management of Diabetes in Long-term Care and Skilled Nursing Facilities: A Position Statement of the American Diabetes Association*. Diabetes Care. 2016)

Criteria	Schedule and Alternative Therapies
Scenarios in Which Deprescribing is a Focus	

 SSI is the only insulin treatment 	
 Discontinue (no taper necessary) If most recent hemoglobin A1C\leq8.5, discontinue SSI without adding treatment If most recent hemoglobin A1C$>$8.5, review average daily insulin requirement over prior 5–7 days, then initiate basal insulin at 50–75% of that average daily insulin requirement

 SSI is used in addition to scheduled basal insulin 	
 Discontinue SSI AND Add 50–75% of the average insulin requirement used as SSI to the current dose of basal insulin -- If postprandial hyperglycemia persists, add either fixed-dose mealtime insulin OR a non-insulin agent (preferably a dipeptidyl peptidase-4 inhibitor or other agent with low hypoglycemia risk)

 SSI is used in addition to scheduled basal insulin AND scheduled mealtime insulin (i.e., correction dose insulin) 	
 Discontinue correction doses AND Add the average correction dose before a meal to the scheduled mealtime insulin dose at the preceding meal -- See Munshi et al. Diabetes Care 2016 position statement for additional details and examples.
Other Scenarios in Which Immediate Deintensification May Be Appropriate	

 SSI is used in short term due to irregular dietary intake or due to acute illness 	
 Discontinue SSI and return to previous regimen once health and glucose levels stabilize Monitor acute illness prior to discontinuation and promote regular dietary intake Short-term use of SSI is appropriate during the episode of acute illness while dietary intake is irregular

 Wide fluctuations in glucose levels in patients with cognitive decline and/or irregular dietary intake on a chronic basis 	
 Order scheduled basal and mealtime insulin based on individual needs with the goal of avoiding hypoglycemia Consider a simple scale such as “give 4 units of mealtime insulin if glucose $>$300 mg/dL” Focus on keeping residents hydrated, especially when glucose levels are high (e.g., $>$300 mg/dL)

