5.2.3. Resident exclusion criteria

1. Life expectancy < 6 months, as indicated by MDS assessment
2. Living in nursing home for less than 30 days
3. Proxy has communicated wish to opt-out of study

Residents *will not* be excluded from the study based on any specific diagnosis (e.g., congestive heart failure or schizophrenia); however, the algorithm used to make recommendations for medication management will consider individual co-morbidities. (see **Table 3** for details)

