4. Staff will be invited to participate in regularly scheduled virtual case based education sessions in order to education staff on falls, deprescribing, osteoporosis, and non-pharmacological management of dementia. Videoconference scheduling and content will be

individualized to participating facilities.

The IP nurse will identify eligible residents for the program. During the startup phase, our study team will assist the local IT Departments in creating a report to calculate the FRAIL score for all long stay residents. These reports will additionally indicate resident age < 60 years and whether a resident has less than a 6 month life expectancy. The IP nurse will use these reports to identify eligible residents and ensure no exclusion criteria. Any resident or proxy who notifies the study team and opts out of study participation, will not be included. The facility champion may also suggest other residents for participation.

The IP nurse will provide recommendations to manage medications. During the qualitative portion of the study, an algorithm will be created that includes evidence based decision making in deprescribing psychotropic and cardiometabolic drugs, as well as patient/proxy preference. We will work with our pharmacist investigator, consultants, and patients/proxies in order to identify the classes of medications we will target for deprescribing. Examples include medications associated with falls (e.g., benzodiazepines, beta-blockers) and medications associated with bone mineral density loss (e.g., proton pump inhibitors). We will use combinations of existing evidence-based tools to develop the deprescribing recommendations including Deprescribing.org (<https://deprescribing.org/resources/deprescribing-guidelines-algorithms/>) and the EMPOWER tool (<https://deprescribing.org/news/empower-trial-empowering-older-adults-to-reduce-benzodiazepine-use/>). Appendix 1 shows a medication algorithm:

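### The beta blocker deprescribing criterion takes in heart-failure use as written, and neither it nor the row for other antihypertensives names CHF exacerbation for chart review

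*Combined protocol and SAP*

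**What the plan says.** Section 5.2.3 states that residents will not "be excluded from the study based on any specific diagnosis (e.g., congestive heart failure or schizophrenia"). It continues, after *however*, that "the algorithm used to make recommendations for medication management will consider individual co-morbidities", and points to Table 3 for details. Section 6.2 places the algorithm in an appendix: "Appendix 1 shows a medication algorithm".

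In Appendix 1, Table 1, the beta blocker criterion is "Used for hypertension OR another indication aside from rate control". The schedule is "50% dose reduction every 2 weeks to discontinuation (over a total of 8 weeks"). The chart-review items at 1 and 4 months are "elevated blood pressure, tachycardia, behaviors, anxiety, functional decline hospitalizations, ED visits".

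The next row is headed as other antihypertensive drugs, with calcium channel blockers, ACE inhibitors and ARBs in brackets. Its one criterion is a systolic pressure below 140 mmHg. The dose is halved every two weeks until the drug is stopped or systolic pressure reaches 141-160 mmHg. Its chart-review items are "elevated blood pressure, tachycardia, functional decline hospitalizations, ED visits".

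**The concern.** Section 5.2.3 names heart failure as a diagnosis that does not exclude a resident and says that the algorithm will weigh co-morbidities. A reader would therefore expect the algorithm's rows for cardiac drugs to separate heart-failure use from use for blood pressure. The beta blocker row does not, and the next row does so at most by implication.

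Two things are at stake. The first is the accuracy of the automated list that starts each recommendation. The second is whether worsening heart failure after one of these tapers would be recorded as consistently as after a diuretic change. The pilot is meant to refine the program before a larger pragmatic trial, so an imprecise rule left in the algorithm could be carried forward.

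**Working it through.** No power or sample-size figure is involved, so the check is a comparison of texts plus one small calculation of cost.

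**1. Selection.**
- *Beta blockers.* The criterion covers hypertension and every other indication except rate control. Heart failure is an indication other than rate control, so it is included. The row has no blood-pressure limit and no co-morbidity condition.
- *Calcium channel blockers, ACE inhibitors, ARBs.* The only stated condition is systolic pressure below 140 mmHg. Taken literally, an ACE inhibitor or ARB given for heart failure meets it. The heading and the blood-pressure endpoint point toward hypertension, so the intent is unclear.
- *Other rows of the same table.* Limits by indication or co-morbidity are already in use. Antiepileptics are tapered only when given for behavioral symptoms of dementia. Antipsychotics for a mental health condition qualify only if it is well controlled, with no psychosis in the past year and a dose above the minimum. Proton pump inhibitors are left alone after a bleeding ulcer or with Barrett's esophagus. A heart-failure limit would match this style.

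**2. Monitoring.**
- The diuretic row lists CHF exacerbation for chart review and adds four weekly weights, with notification at a gain of 5 lb.
- Neither of the two rows at issue lists CHF exacerbation or weights. Nursing checks in both concern raised blood pressure (two or more systolic readings above 160 mmHg).
- Sections 2.4 (Safety) and 7.3 list the targeted events for cardiometabolic deprescribing as unplanned visits for hypertension, tachycardia or hyperglycemia. Heart failure is absent. Targeted events are the ones those sections send for causality assessment with the Drug Withdrawal Probability Scale.

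**3. Cross-reference.** The Table 3 cited in Section 5.2.3 should hold the co-morbidity details. The only table with that number in the text available is "Table 3. Sliding Scale Insulin". The pointer is probably meant for Appendix 1, Table 1, though the documents do not say so.

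**4. Cost of a limit.**
- Inputs: about 80 high-risk residents (Section 2.6) and a 50% target for those with a deprescribing recommendation (Section 2.4, Table 1).
- Target count: 0.50 × 80 = 40 residents.
- Change for each resident who loses the only deprescribing recommendation: 1/80 = 0.0125, or 1.25 percentage points.
- An osteoporosis recommendation would not keep that resident in the Table 1 measure. It would under the Demand paragraph of Section 2.4, which counts either type.

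**The case against.** The strongest reply is that co-morbidity is handled by people as well as by the table. Table 2 in Section 6 has the automated step identify only possible candidates. Under Section 6.2 the nurse reviews the medical record for every eligible resident, supported by geriatricians and a pharmacist, and the primary provider may modify the plan before signing. Section 8.2 requires the provider's agreement to each change. All of this stands. A reader might infer that the protocol orders heart-failure drugs to be stopped, and the documents do not support that. The program also encourages acceptance, through monthly adherence feedback (Section 6.2) and refinement until more than 50% of recommendations are accepted (Section 10). That is a reason to have the starting list right.

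A reader might also infer that worsening heart failure would go unseen. It would not. Both rows review functional decline, hospitalizations and ED visits. Section 9 counts worsening of an existing disease that leads to an unplanned visit as a study-related adverse event, and provides for quarterly MDS review of serious events. Weekly huddles (Section 7.3) and a study phone number (Section 8.2) add early reporting. What is missing is a named item.

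Three further limits stand:
- The heading of the second row can fairly be read as restricting it to hypertension, so the selection finding is firm only for beta blockers.
- It is tempting to say that the diuretic row monitors heart failure while excluding heart-failure use. Its last limb, about other classes not having been tried, may stand alone in the flattened table, so that contrast and any count of rows are unsafe.
- Section 5.2.3 joins its two statements with *however*. That the algorithm is the reason for having no exclusion is an inference.

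**Conclusion.** The point holds as a minor safety gap. The beta blocker criterion, read literally, flags heart-failure use for taper to discontinuation, despite the assurance in Section 5.2.3. The criterion for calcium channel blockers, ACE inhibitors and ARBs needs clarifying. CHF exacerbation is named in neither row's chart review nor among the targeted cardiometabolic events.

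No sample size or planned analysis is affected. The practical importance rests on the assumption that some eligible residents take these drugs for heart failure. The documents give no number, so none is claimed. That such events would be recorded less consistently than after a diuretic change is a reasonable expectation, not a demonstrated result.

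**What to change.** 1. Change the beta blocker criterion to read *aside from rate control or heart failure*. The team can still recommend a change case by case.
2. Clarify the criterion for calcium channel blockers, ACE inhibitors and ARBs as *used for hypertension, not heart failure, with SBP <140 mmHg*.
3. Add CHF exacerbation to the 1- and 4-month chart-review items of both rows. This remains useful after the first two changes, because a resident with heart failure may have the drug recorded for hypertension.
4. Correct the Table 3 pointer in Section 5.2.3, probably to Appendix 1, Table 1, once the study team confirms the intended target.

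The cost is a few words, one review item in each row and an update to the automated screen. Section 7.3 already abstracts active diagnoses at baseline, so no new data source is needed. Slightly fewer residents may be flagged, at the 1.25 points each worked out above. Residents with another deprescribing recommendation do not change the Section 2.4, Table 1 measure.

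### The sliding-scale insulin conversions can start or raise scheduled insulin, but no hypoglycemia item is described in the matching monitoring cells or the targeted adverse events, so lows managed in the facility reach the safety data only by chance

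*Combined protocol and SAP*

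**What the plan says.** The SSI row of Appendix 1, Table 1 and the scenarios in Appendix 1, Table 3 set out what replaces sliding-scale insulin.

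- **SSI as the only insulin, A1C above 8.5:** take the average daily requirement over the prior 5–7 days, "then initiate basal insulin at 50–75% of that average daily insulin requirement". At A1C 8.5 or below, nothing is added.
- **SSI plus basal:** "Add 50–75% of the average insulin requirement used as SSI to the current dose of basal insulin". If post-meal glucose stays high, add either fixed mealtime insulin or a non-insulin agent, "preferably a dipeptidyl peptidase-4 inhibitor or other agent with low hypoglycemia risk".
- **SSI plus basal plus mealtime:** "Add the average correction dose before a meal to the scheduled mealtime insulin dose at the preceding meal".
- **Wide glucose fluctuations:** "Order scheduled basal and mealtime insulin based on individual needs with the goal of avoiding hypoglycemia".

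Monitoring in the SSI row has two glucose-specific parts. The nurse order is "Nursing will measure fasting blood sugar daily for 2 weeks. Notify MD/NP for any BG >300 or >2 values over 200". The 1- and 4-month chart review looks for "severe hyperglycemia (>400), polydipsia, polyuria, functional decline hospitalizations, ED visits".

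For cardiometabolic deprescribing, the targeted adverse events in Sections 2.4 and 7.3 are unplanned visits for high blood pressure, fast heart rate or high glucose. Section 8.2 repeats these as risks. Targeted events go into REDCap and then to a review of their relation to the medication change.

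The protocol does treat low glucose as something to avoid. The sulfonylurea/meglitinide row states: "Goal is to achieve hemoglobin A1C 8-9 AND no episodes of severe hypoglycemia or severe hyperglycemia".

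**The concern.** Aim 2b evaluates safety. When the study recommends a new or higher scheduled insulin dose, low glucose is the drug's own adverse effect, and the protocol itself sets goals of avoiding it. Yet the places where events are watched for and counted point only upward. A low that nursing staff treat on the unit, without a visit or transfer, is not a targeted event, so it is not directed into REDCap or the relatedness review. If the pilot then reports no hypoglycemia after insulin changes, a reader could not tell whether none occurred or none was recorded.

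**Working it through.** The plan gives no figure to reproduce here. The check is dose arithmetic followed by a comparison of the monitoring text.

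**1. Does scheduled insulin start or rise?** Let S be the average daily SSI dose, B the current basal dose and C the average correction dose. The percentages are those in Appendix 1, Table 3.

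| Scenario | Change in scheduled insulin | Change in total insulin |
|---|---|---|
| SSI only, A1C ≤8.5 | none | −S |
| SSI only, A1C >8.5 | 0 to 0.50S–0.75S | −0.25S to −0.50S |
| SSI + basal | +0.50S to +0.75S | −0.25S to −0.50S, before any mealtime add-on (dose not stated) |
| SSI + basal + mealtime | +C at the preceding meal | about 0 (C is moved, not added) |
| Short-term SSI | return to previous regimen | not applicable |
| Wide fluctuations | individual; prior regimen and direction not stated | not stated |

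Illustration with assumed doses:
- B = 20 and S = 10 units/day: scheduled insulin goes from 20 to 20 + 0.50×10 = 25, or to 20 + 0.75×10 = 27.5 (up 5/20 = 25% to 7.5/20 = 37.5%). The total goes from 30 to 25–27.5.
- SSI alone at 10 units/day, A1C >8.5: scheduled insulin goes from 0 to 5–7.5, and the total from 10 to 5–7.5.

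So three conversions start or raise scheduled insulin, and the wide-fluctuations scenario may. In the three, the total falls or is about unchanged unless mealtime insulin is added.

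**2. Do the SSI-row monitoring cells name low glucose?**
- Chart review: glucose above 400, thirst, urination, function, hospital and emergency visits. No.
- Nurse notification: any value above 300, or more than two above 200. No lower limit.

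The nurse order yields up to 7 × 2 = 14 fasting readings per resident. A low fasting value may therefore already be in the chart, but nothing asks for it to be reported or abstracted. Fasting checks over 2 weeks would not show later lows or those at other times of day.

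**3. Do the event lists name it?** Sections 2.4 and 7.3 carry nearly the same list, and 8.2 restates it. None names hypoglycemia. The withdrawal-symptom list in Section 9 does not either; its nearest term is a worsening of underlying disease.

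**4. How does the protocol monitor other drugs it starts?** Appendix 1, Table 2 names the drug's own harms: raised calcium for calcium and vitamin D; reflux, esophagitis and low calcium for antiresorptives. The SSI row can also start or raise a drug but does not follow that pattern.

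**5. What else could catch a low?**
- Hospital and emergency visits (7.3) and life-threatening events (9): these capture severe lows.
- An unplanned provider visit (9): possibly.
- General adverse-event review of the chart and weekly huddles (7.3), staff reporting through the champion (6.2), EMR and quarterly MDS data on new or unstable conditions (8.1), communication channels (8.2), and prompt reporting of safety events to the investigators (9): non-specific, with no low-glucose item described.

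**6. How many residents?** The documents do not say. If 0% to 20% of the roughly 80 residents had any glucose-lowering change (an assumption), that is 80×0 = 0 to 80×0.20 = 16. Those given new or higher scheduled insulin are a smaller subset that could be near zero.

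**The case against.** The strongest defence is that this is a deprescribing protocol and its rows coherently watch for withdrawal effects. The antihypertensive row, for example, lists no hypotension. The main conversions do not raise total insulin, a provider must review and sign each change (Sections 6.2 and 8.2), and several general reporting routes exist. Analysis is largely descriptive, with no hypoglycemia count planned and no stopping rule, so no planned result changes. The REDCap form is not in the documents, so a field may exist that the text does not describe.

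Most of this stands and keeps the point small. It does not close the gap: the general routes depend on someone choosing to report a low, and the events directed to relatedness review are a named list without it.

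A reader might infer more than the documents support:
- **That the algorithm raises hypoglycemia risk.** The documents do not say so. Section 2.2 mentions hypoglycemia as a reason why deprescribing should help these residents more.
- **That severe lows go unseen.** Those leading to hospital or emergency care are collected.
- **That the sulfonylurea/meglitinide row has the same fault.** Its monitoring is also upward-only, but it starts no insulin; its substitute is a DPP-4 inhibitor.
- **That three separate event lists fail.** They are largely one list repeated.
- **That wide fluctuations is a fourth insulin increase.** It sits among the deintensification scenarios and does not say that the dose rises.

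**Conclusion.** The point holds as a minor gap in safety ascertainment. Three conversions direct new or higher scheduled insulin, and a fourth scenario may. Neither of the two SSI-row monitoring cells nor the targeted adverse event list names low glucose, and no hypoglycemia item is described elsewhere. In-facility lows after a study-recommended insulin change therefore cannot be counted reliably. This rests on reading the protocol as written, since the abstraction form is not available. The number of residents affected is unknown, and the 0-to-16 range is an assumption. Nothing here shows that residents would be harmed or that any planned analysis is invalid.

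**What to change.** Make two changes:

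1. Add one item, documented hypoglycemia (yes/no, date), to the existing 1- and 4-month chart abstraction for residents with a study-recommended insulin change. The medication and dose data already collected under Section 7.3 identify them.
2. List hypoglycemia for these residents as its own targeted adverse event in Sections 2.4 and 7.3, with a matching entry in 8.2, so that it enters REDCap and the relatedness review. Do not place it under the unplanned-visit wording of 2.4 and 7.3, which would count visits and still miss lows that nursing staff manage.

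No new test, glucose threshold or dose is proposed.

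Cost: a short amendment and a few minutes of abstraction per affected resident. At the upper end of the assumed range, 16 residents × 2 reviews = 32 reviews. At an assumed 2 to 5 minutes each, that is 32×2 = 64 to 32×5 = 160 minutes in total, beside the 15 minutes per patient that Table 2 in Section 6 already allots to the 1- and 4-month review.

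Limits: only charted lows are counted, a count does not establish cause, and if few residents have an insulin change the item costs and yields little.
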